13.3 Exploratory efficacy endpoints

13.3.1 Adaptive behavior composite score

This endpoint will be obtained with the adaptive behavior composite score of VABS-II. Change from Baseline will be assessed at Week 24.

13.3.2 Neurocognitive composite score

This endpoint will be obtained with the cognitive subtest score of BSID-III or the mental processing composite score as assessed by KABC-II.

Change from Baseline will be assessed at Week 24.

13.3.3 Language

Expressive and receptive language is assessed by the BSID-III language subtest score and the VABS-II communication domain score, respectively.

For patients being assessed with the KABC-II for cognition, language development is assessed by the subtest “Expressive Vocabulary” of the knowledge test.

In addition, written language is assessed by the AEQ of subdomain “Written” in the communication domain of VABS-II.

Changes from Baseline will be assessed at Week 24.

13.3.4 Motor function

Fine and gross motor skills are assessed by the total scores of the BSID-III corresponding subtests of the motor function module, and by the AEQ of the VABS-II motor skills domain.

Changes from Baseline will be assessed at Week 24.

13.3.5 Sleep pattern

The patients' sleep pattern is evaluated using the CSHQ total score and by use of actigraphy.

An actigraph (ActiGraph GT9X Link) will be applied to the non-dominant wrist or ankle (9) and recordings will be made for 7 consecutive days and nights at Baseline and at Weeks 11 and 23. A daily wear time of 20 hours per day will be regarded as a compliant recording. The recording will be supported by an actigraph log, recorded in the eCRF.

The following parameters will be determined on the basis of recordings in the actigraph log:

- Bedtime (Clock time child is put to bed)
- Wake time (Clock time of child is taken out of bed)
- Time in bed (Time between Bedtime and Wake time)

The following variables are derived as obtained from the actigraph software:

- Sleep onset (Clock time for first appearance of a predetermined number of consecutive min of sleep)
- Sleep offset (Clock time for last of a predetermined number of consecutive min of sleep)
- Sleep period (Time between sleep onset and sleep offset)
- Total sleep time (TST, Duration of sleep in sleep period)
- Wake after sleep onset (WASO, number of minutes scored as wake during sleep period)
- Sleep efficiency (Percentage sleep: TST/time in bed)
- Night waking frequency (number of night wakings)
- Night waking duration (Sum of minutes scored as night waking)
- 24 h sleep duration (amount of sleep in a 24-h period)

Sleep onset latency is determined as Time between bedtime (as recorded on the actigraph log) and sleep onset (as captured by the actigraph software).

Changes from Baseline will be assessed at Week 12 and 24.

For more details regarding the methods used by the actigraph software please see the CSP for SOB003-001, Section 7.5.4.5.

13.3.6 Magnetic resonance imaging

As listed in Section 3.4.3, the MRI exploratory endpoints refer to compound ventricular volume, FA and MD in corpus callosum, FA and MD of cerebral white matter, SWI in cerebral white matter, and basal ganglia. Also liver and spleen volume are assessed by abdominal MRI.

Changes from Baseline (as defined in Section 8.4.3) will be assessed at Week 24.

13.4 Subgroup analyses

No subgroup analyses will be performed for any of the efficacy analyses.

14 Safety analyses

Safety data will be summarized descriptively by dose cohort using the SAF.

14.1 Drug exposure

Upon provision of signed informed consent, patients are assigned a patient number and allocated to a dose cohort in strict consecutive order. Thus, the first 3 enrolled patients are assigned to Cohort 1 and administrations of SOBI003 at 3 mg/kg/week; for Cohorts 2 and 3, dose levels of 10 mg/kg/week and 20 mg/kg/week are planned.

At the time of the 1st SOBI003 infusion, the patient should not have any clinically significant evidence of an ongoing infection, or an ongoing treatment with antibiotics. In such cases, the 1st infusion should be postponed until the infection has resolved.

SOBI003 is administered as weekly i.v. infusions over a period of time of 4 hours. The study treatment period comprises 24 weekly infusions. For each weekly visit, date and time of administration will be recorded in the eCRF, as well as reasons for infusion stop (if any), dose level, SOBI003 volume, total infusion volume administered, and dosing action taken (e.g., “withdrawn”). All data will be listed.

In addition, actual dose received in mg, actual dose level received in mg/kg (see Section 8.4.8), and study treatment exposure in weeks will be calculated (see Section 8.4.2). These data will be listed and summarized.

14.2 Adverse events

The primary endpoints are TEAEs and SAEs.

For the FIH study (SOBI003-001), all AEs (defined in CSP Section 7.5.5.1.1) occurring after the patient has received the 1st dose of investigational medicinal product and up to Day 7 of Week 24 (End of Study) will be recorded on the AE eCRF page.

For the FIH study, SAEs will be reported from the time the ICF is signed until 28 days past the last dose of study drug.

For patients continuing in the extension study (SOBI003-002), the period for recording AEs, including SAEs, on the eCRF begins Day 1 upon signing of the study ICF on Week 25 and ends Day 8 of Week 104 (End of Study) (see CSP Section 7.5.4.1.2). This includes all events observed/diagnosed or reported since the last visit of the FIH study (Week 24 / End of study).

For patients continuing in the extension study (SOBI003-002), any AEs and SAEs with onset after the 1st dose of study drug in the extension study will not be presented in the tables and listings of the FIH study but in the tables and listings of the extension study.

A TEAE is any AE with onset or worsening reported from the time that the 1st dose of study drug is administered until completion of or early termination of the study. In addition to TEAEs, SAEs with an onset date equal to or greater than the informed consent date of the FIH study and earlier than the start date of 1st dose of study drug (non-treatment emergent) will be collected and analyzed.

AEs with missing onset dates will be considered treatment-emergent, unless the stop date indicates otherwise. In the event that only a partial start date (month/year) is available, and

month/year occurs before that of 1st dose of study drug, the AE will be considered as non-treatment-emergent. If month/year occurs on, or after that of 1st dose of study drug, the AE will be considered as treatment emergent. If an AE has a partial missing start or stop date, the rules in Section 8.1 will be used to impute the date.

All AEs will be coded using MedDRA to give a PT and a SOC term for each event. The latest version of MedDRA will be used.

The severity grading is based on the national cancer institute common terminology criteria (NCI CTCAE) (version 4.03), see CSP Section 7.5.5.13.

If the causality assessment (related, not related) of a TEAE is missing, the event will be considered as drug-related following the worst case principle. Non-treatment emergent SAEs with missing causality assessment are considered not related.

An Infusion related reaction (IRR) has been defined as any AE occurring during an infusion or within 24 hours after end of infusion and which is considered related to SOBI003 treatment as judged by the investigator. IRRs may appear as symptoms such as rash, urticaria, erythema, emesis, loose stools, fever, alterations in heart rate, and blood pressure, but could also include other symptoms considered related to the infusion. Such symptoms (by PT and SOC) will be grouped into separate IRRs. There can be one IRR per infusion, in case several IRR symptoms are reported for one infusion they will be counted as one single IRR.

TEAEs will also be classified according to the patients ADA status (positive, negative, boosted, unknown) at the time of the AE occurrence.

All AEs will be summarized by dose cohort. The following analyses will be performed:

- Overall summary of AEs (overall, non-treatment emergent SAEs, TEAEs, drug-related TEAEs, non-serious TEAEs, serious TEAEs, serious drug-related TEAEs, TEAEs leading to study and/or treatment withdrawal, drug-related TEAEs leading to study and/or treatment withdrawal, serious TEAEs leading to study and/or treatment withdrawal, TEAEs leading to death, IRRs)
- Overall summary of IRRs (overall, serious IRRs, IRRs leading to study and/or treatment withdrawal). There can be one IRR per infusion, in case several IRR symptoms are reported for one infusion they will be counted as one single IRR.
- TEAEs by SOC and PT
- TEAEs by SOC and PT and by maximum CTCAE grade
- Drug-related TEAEs by SOC and PT
- Drug-related TEAEs by SOC and PT by maximum CTCAE grade
- Serious TEAEs by SOC and PT
- Serious TEAEs by SOC and PT by maximum CTCAE grade
- Serious drug-related TEAEs by SOC and PT
- Serious drug-related TEAEs by SOC and PT by maximum CTCAE grade
- TEAEs leading to study and/or treatment withdrawal by SOC and PT
- TEAEs leading to study and/or treatment withdrawal by SOC and PT by maximum CTCAE grade

- Drug-related TEAEs leading to study and/or treatment withdrawal by SOC and PT
- Drug-related TEAEs leading to study and/or treatment withdrawal by SOC and PT by maximum CTCAE grade
- TEAEs by SOC and PT and by ADA status
- IRR symptoms by SOC and PT
- IRR symptoms by SOC and PT by maximum CTCAE grade
- Serious IRR symptoms by SOC and PT
- Serious IRR symptoms by SOC and PT by maximum CTCAE grade
- IRR symptoms leading to study and/or treatment withdrawal by SOC and PT
- IRR symptoms leading to study and/or treatment withdrawal by SOC and PT by maximum CTCAE grade
- Frequency of IRR symptoms resolved within 24 hours.

For each SOC and PT, summaries will be made with respect to the proportion of patients having a least one occurrence of that event and the total number of events, with the exception of tables by maximum CTCAE grade (which include only the proportion of patients having at least one occurrence of that event). Tables will be sorted alphabetically, first by SOC and then by PT.

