7.5.1.13 Treatment Withdrawal

If the patient is withdrawn from study treatment, the patient should be examined as soon as possible after making the withdrawal decision. Adverse events and use of concomitant medications are captured. Blood and urine are collected for safety laboratory, immunogenicity, HS and PK assessments. When separate consent for future research has been provided, blood and urine are also collected for storage at the central laboratory for future biomarker research, and if the patient is also withdrawn from the study blood is collected for future genetic research. Vital signs are assessed and a neurological and a physical examination are performed. A 12-lead ECG is obtained and an echocardiography is performed. Height, weight and head circumference are obtained. Additional safety assessments will be performed at the discretion of the investigator, as warranted by any AE(s) leading to treatment withdrawal.

When possible, non-infusion-related study assessments should continue in accordance with the Schedule of Events (refer to Table 3) until completion of the Week 24 visit. At minimum, the Early Termination assessments should be repeated 30 to 40 days after the last SOBI003 administration. Patients with ADA-positive samples should continue to be followed in accordance with Sections 7.5.5.3 and 7.5.6.1.

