- Results in persistent or significant disability/incapacity.
- Is a congenital anomaly/birth defect (i.e., in an offspring to the study subject).

Other medically important adverse events that may not result in death, be life threatening, or require hospitalization may be considered serious when, based upon appropriate medical judgment, they may jeopardize the patient or subject or may require medical or surgical intervention to prevent one of the outcomes listed above. Examples of such events are intensive treatment in an emergency room or at home for allergic bronchospasm, blood dyscrasias or convulsions that do not result in hospitalization or development of dependency or abuse.

Serious also includes any other event that the investigator or company judges to be serious. Any suspected transmission of an infectious agent via IMP shall also be considered serious.

Hospitalization

Hospitalization includes transfers within a hospital (e.g. from the hospital ward to the intensive care unit) and also includes admissions less than 24 hours. The following situations are not considered hospitalizations (although other SAE criteria may still apply):

- Outpatient procedures / ambulatory care.
- Emergency department visits.

Hospitalization in the absence of an adverse event occurring during the study should not be considered an SAE. This includes:

- Hospitalization due to a pre-existing condition not associated with a worsening of the pre-existing condition.
- Protocol specified admission.
- Elective admission, e.g. due to cosmetic surgery.
- Pre-planned admission for a condition specified at Baseline for the patient.

[figure not shown]
Treatment-emergent adverse event (TEAE)

TEAE is any AE with onset or worsening reported from the time that the first dose of IMP is administered until completion of or withdrawal from the study.

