7.5.5.1.2 Adverse event reporting period

The period for recording adverse events, including SAEs, on the CRF begins upon receiving the first dose of investigational medication and ends at completion of the Week 24 visit.

In addition, SAEs should be reported, from the time the ICF is signed until 28 days past the last dose of IMP. Furthermore, any SAE should be reported to Sobi irrespective of the time of occurrence if a causal relationship between the event and the IMP(s) is suspected.

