7.5.5.1.5 Follow-up of unresolved adverse events

All adverse events should be followed until they are resolved or the investigator assesses them as chronic or stable, or the patient's participation in the study ends, i.e., until completion of the Week 24 visit. For patients entering the extension study, all AEs and SAEs occurring after Week 24 visit, should be noted in the extension study SOBI003-002. How to report changes in an ongoing adverse event during a patient's participation in the study is described in the CRF instructions.

In addition, all serious and non-serious adverse events assessed by the investigator as related to SOBI003 should continue to be followed until they resolve or until the investigator assesses them as "chronic" or "stable", even after the patient's participation in the study is over.

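### The TEAE window closes at the end of the study while SAEs are collected to 28 days after the last dose, so a late SAE has no defined category in the primary-endpoint tables

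*SAP*

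**What the plan says.** SAP 14.2 states: "The primary endpoints are TEAEs and SAEs". Three rules then decide which events reach the tables.

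- **TEAE window.** The SAP counts events with onset or worsening "from the time that the 1st dose of study drug is administered until completion of or early termination of the study". Protocol 7.5.5.1.1 has "from the time that the first dose of IMP is administered until completion of or withdrawal from the study". SAP 14.2 places the end of study at Day 7 of Week 24, and protocol 7.5.5.1.5 ends participation when the Week 24 visit is complete.
- **SAE collection.** SAP 14.2 says "SAEs will be reported from the time the ICF is signed until 28 days past the last dose of study drug". Protocol 7.5.5.1.2 gives the matching span: "from the time the ICF is signed until 28 days past the last dose of IMP".
- **SAEs that are not TEAEs.** SAP 14.2 adds one class only, SAEs from consent that start "earlier than the start date of 1st dose of study drug (non-treatment emergent) will be collected and analyzed".

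The tables planned in SAP 14.2 by system organ class and preferred term cover serious TEAEs. The overview table has rows for TEAEs, serious TEAEs, non-treatment-emergent SAEs and a row called 'overall', which is not defined. SAP 14.2.1 lists all SAEs.

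For children who roll over, protocol 7.5.5.1.5 says "all AEs and SAEs occurring after Week 24 visit, should be noted in the extension study SOBI003-002". SAP 14.2 has the extension eCRF pick up everything since the last visit of this study, but removes an event from this study's tables and listings only if it began after the first extension dose. SAP 4.1 reports that 3 children were included in each of Cohorts 1 and 2, that all had enrolled in the extension, and that Cohort 3 will not start.

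**The concern.** The collection window and the analysis window for one primary endpoint end on different dates, and no category covers the difference. An SAE in that tail is neither a serious TEAE nor a pre-dose SAE. In a cohort of 3, one such event is the difference between 1/3 and 0/3 in a serious-TEAE row.

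Two other rules in SAP 14.2 make the omission harder to program around. An event dated only to month and year is treatment-emergent if that month is on or after the first dose, with no upper bound, so a poorly dated tail SAE would count while a fully dated one would not. Missing causality is set to related for TEAEs and to not related for non-treatment-emergent SAEs, so a tail SAE has no rule.

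For a child who rolls over, an event between the Week 24 Day 7 visit and the first extension infusion is recorded in the extension, stays by implication in this study's outputs, and lies outside this study's TEAE definition.

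**Working it through.** The plan states no figure on this point, so there is none to reproduce. The check is study-day arithmetic on the nominal schedule.

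**Inputs.** Weekly infusions with Day 1 of Week 1 as the first (protocol 7.4.6 and 7.5.1.4); end of study at Week 24 Day 7 (SAP 14.2); SAE collection to last dose + 28 days (SAP 14.2, protocol 7.5.5.1.2); first extension infusion on Day 8 of Week 24 (SAP Table 3, footnote h).

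**Formulas.** Study day of week w, day d: 7(w − 1) + d. Tail = max(0, last-dose day + 28 − end-of-study day).

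**End of study.** 7 × 23 + 7 = Day 168.

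**Child who stays to Week 24 and does not enter the extension:**

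| Last infusion | Day given | Day + 28 | Tail beyond Day 168 |
|---|---|---|---|
| 20 | 134 | 162 | 0 |
| 21 | 141 | 169 | 1 |
| 22 | 148 | 176 | 8 |
| 23 | 155 | 183 | 15 |
| 24 | 162 | 190 | 22 |

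So a completer has 22 of 28 days outside the TEAE window. If the Week 24 visit closes 7 days later, under the +7-day allowance for the cognitive tests (SAP Table 3, footnote i), this falls to 22 − 7 = 15.

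**Child who leaves the study on the day of the last dose:** up to 28 of 28 days outside.

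**Child who rolls over:** the first extension infusion is on 7 × 24 + 1 = Day 169, so the gap is 169 − 168 = 1 day nominally, or 1 + k days if that infusion is delayed by k days. This is the only line that applies to the 6 analysed children; 0 of 6 belong to the other groups.

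**Testing two possible end dates for the window.** A child who stops treatment is asked to continue assessments to Week 24 when possible (protocol 7.3.3.1 and 7.5.1.13) and is covered to Day 168 today.

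- Last infusion number 4, Day 22: a plain rule of last dose + 28 ends on Day 50 and loses 168 − 50 = 118 days. The later-of rule gives max(168, 50) = Day 168, with no loss.
- Last infusion number 12, Day 78: the plain rule ends on Day 106 and loses 168 − 106 = 62 days. The later-of rule again gives Day 168.
- Completer, not rolling over: max(168, 190) = Day 190, so the tail is closed.
- Rollover child: the later-of rule gives Day 190, cut immediately before Day 169, so the 1-day gap is closed without overlapping the extension.

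**The case against.** The strongest case against the point is that nobody is in the tail. With all 6 children in the extension, the 22-day and 28-day figures describe no one in the planned analysis. That stands, and it limits the point to a definition with a small expected effect.

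Three stronger readings are tempting, and the documents do not support them.

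- **A reader might infer that tail SAEs go unreported.** They do not. SAP 14.2.1 lists all SAEs, Listing 16.2.7 covers all adverse events, and the 'overall' row may count them. Protocol 7.5.5.1.2 also requires any SAE suspected to be related to be reported whenever it occurs, and protocol 7.3.3.2 continues follow-up of events that led to withdrawal. What is missing is a defined table category.
- **A reader might infer that children who stop because of a reaction are the ones whose events drop out.** The window closes on leaving the study, not on stopping treatment. A child who stops at infusion 20 or earlier and stays to Week 24 has no tail. For children who stop treatment, protocol 7.5.1.13 adds: "At minimum, the Early Termination assessments should be repeated 30 to 40 days after the last SOBI003 administration".
- **A reader might infer that the rollover rules flatly contradict each other.** Most of the difference is between where an event is recorded and where it is presented, and SAP 8 describes one combined database. What remains is that an event before the first extension dose is kept for presentation here while the TEAE definition leaves it out.

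**Conclusion.** The point holds as a gap in the definition of the primary endpoint. A fully dated SAE after the end of study and within 28 days of the last infusion fits neither SAE class that the SAP tabulates. For a completer who does not roll over, the exposed period is 22 of 28 days (15 if the Week 24 visit closes 7 days late), and for a child who leaves at the last dose it is up to 28. For the 6 children to be analysed it is the interval from Week 24 Day 7 to the first extension infusion, nominally 1 day.

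This rests on the nominal weekly schedule, on SAP 4.1 being correct that every child entered the extension, and on reading 'early termination of the study' as leaving the study. Protocol 7.5.5.1.1 supports that reading, although the SAP's schedule footnotes use early termination for stopping SOBI003 treatment. The expected effect on the 6-patient report is small. The correction is worth making because it is cheap and because the rollover rule applies to every analysed child.

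**What to change.** In SAP 14.2, with matching wording in protocol 7.5.5.1.1, define the TEAE window as running from the first dose to the **later** of study completion or withdrawal and 28 days after the last SOBI003 infusion. For a child who enters the extension, end it immediately before the first extension infusion. Use that same cut-off to assign events to this study or the extension; SAP 11 already uses the first extension dose in this way for medications.

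The rule must not end simply at 28 days after the last infusion, because that would shorten coverage for children who stop treatment but stay to Week 24. State that early termination here means leaving the study, apply the same upper bound to partly dated events, and define the 'overall' row. Protocol 7.5.5.1.2 stops routine AE recording at the Week 24 visit, so for children who do not roll over a table footnote should say that the window after that visit captures SAEs only.

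The cost is a wording change and one derivation rule. No new data are needed for the 6 children, and reported incidence can only stay the same or rise slightly.

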7.4 Immunogenicity analysis set

The immunogenicity set will consist of those patients in the safety analysis set who have sufficient blood samples taken for ADA testing at baseline and at least 1 post-dose time-point.

The immunogenicity set will be used for the immunogenicity analyses.

In case any patient has missing baseline, a second immunogenicity analysis set will be formed including all patients with sufficient blood samples for ADA testing (i.e. including those with missing baseline). All immunogenicity analyses without considering baseline will be performed on that second set.

8 General issues for statistical analysis

All statistical tests will be two-sided and performed using a 5 % significance level, if not stated otherwise. Results will be presented as the estimated mean value for each treatment group, the estimated difference between groups, the associated 95 % two-sided confidence interval and P-value. P-values from statistical analyses will be presented to three decimal places with values below 0.001 displayed as <0.001 and confidence intervals will be presented to one more decimal places than the raw data.

Continuous data will be summarized using descriptive statistics: number of patients (n), mean, standard deviation (SD), standard error of the mean (SE), median, minimum and maximum values, unless otherwise indicated. Minimum and maximum values will be presented to the same number of decimal places as the raw data and mean, SD, SE of the mean and median will be presented to one more decimal place than the raw data. Summary tables over all patients will include in addition the first quartile (Q1) and the third quartile (Q3), presented to one more decimal place than the raw data.

Categorical data will be summarized using frequency counts and percentages. Percentages will be suppressed when the count is zero, however the category will still be displayed. The denominator for all percentages will be the number of patients within the treatment group for the population of interest, unless otherwise indicated. Percentages will be presented to one decimal place.

Data for the FIH SOBI003-001 study (up to Week 24) and extension study SOBI003-002 (Week 25 to 104) will be collected in a combined database. All analyses specified in this SAP refer to FIH study SOBI003-001, i.e. for data up to Week 24.

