8.4.2 Study treatment exposure

For patients who continued study treatment until end of the study SOBI003-001, study treatment exposure in weeks will be calculated as ([date of last visit attended – date of 1st infusion of study treatment] + 1) / 7, rounded to the nearest decimal.

For patients who stopped study treatment during the course of the study, study treatment exposure in weeks will be calculated as ([date of last infusion + 7 days – date of 1st infusion of study treatment] + 1) / 7, rounded to the nearest decimal.

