14.5 Immunogenicity

Serum samples are collected at Baseline (same time as the CSF sample is collected) and prior to start of SOBI003 infusion at Weeks 2, 4, 8, 12, 16, 20, and 24, and if applicable at Early Termination of SOBI003 treatment, CSF samples (0.5 mL) are collected at Baseline and at Weeks 12 and 24.

The analysis of immunogenicity will in general be based on the immunogenicity analysis set. In case any patient has missing baseline, all immunogenicity analyses without considering baseline will be performed on a second immunogenicity analysis set including all patients with sufficient blood samples for ADA testing (i.e. including those with missing baseline).

The analyses of PK by ADA status at baseline will be based on the PKAS.

The following definitions will apply as defined in the harmonized terminology for immunogenicity (10):

- **Evaluable patient:** A patients with at least 1 sample taken after study drug administration that is appropriate for ADA testing (with reportable result).
- **ADA-positive sample:** When ADA is detected in a sample, the sample is considered positive.
- **Baseline ADA:** Pre-existing antibodies detected at baseline.
- **Treatment induced ADA:** de novo development following administration of study drug (i.e., formation of ADA any time after the initial study drug administration in a patient without preexisting ADA).
- **Treatment boosted ADA:** Baseline ADA boosted to higher level following study drug administration (i.e., at any time after the initial study drug administration the ADA titer is greater than the baseline titer by a factor of four).
- **ADA-positive patient:** A patient with at least 1 treatment-induced or treatment-boosted ADA-positive sample at any time during the treatment or follow-up observation period.
- **ADA-negative patient:** A patient without a treatment induced or treatment-boosted ADA-positive sample during the treatment or follow-up observation period.
- **Baseline ADA positive patient:** A patient with ADA at baseline. Such patient can have treatment boosted ADA after dosing.

Note that the requirement for inclusion in the immunogenicity set of at least 1 post-dose ADA assessment means that all patients in the immunogenicity set are “evaluable patients”.

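### TEAEs are tabulated by ADA status without time at risk in each status, so the counts partly reflect how long each status lasted

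*SAP*

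**What the plan says.** SAP Section 14.2 states that "TEAEs will also be classified according to the patients ADA status (positive, negative, boosted, unknown) at the time of the AE occurrence". Status is thus attached to the event, not the patient, and one patient can contribute events to more than one status. The list of analyses in the same section includes "TEAEs by SOC and PT and by ADA status"; the index in SAP Section 19.2 gives this as Table 14.3.1.14, by title only.

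The measures are set at the end of Section 14.2: "summaries will be made with respect to the proportion of patients having a least one occurrence of that event and the total number of events". The general rule in SAP Section 8 is: "The denominator for all percentages will be the number of patients within the treatment group for the population of interest, unless otherwise indicated". Neither Section 14.2 nor Section 14.5 (Immunogenicity) indicates another denominator for this table.

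Exposure is defined for the treatment period as a whole. For patients who stay on treatment, SAP Section 8.4.2 says "study treatment exposure in weeks will be calculated as ([date of last visit attended – date of 1st infusion of study treatment] + 1) / 7". Nothing divides weeks or infusions by ADA status.

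Serum ADA is sampled at Baseline and "prior to start of SOBI003 infusion at Weeks 2, 4, 8, 12, 16, 20, and 24" (SAP Section 14.5), so consecutive on-treatment samples are two to four weeks apart. The SAP gives no rule for a patient's status between samples.

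**The concern.** The numerator is split by a status that changes over time and the denominator is not. A patient who converts early has few weeks in which to have an event while negative and many while positive. The count columns then differ even if antibodies do nothing. The percentage columns have the same fault, and a second one: by default they include patients who were never in the status.

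At stake is how the reader judges the influence of antibodies on safety. Protocol Section 5.3 describes immune-mediated reactions as common with lysosomal enzyme replacement and possibly severe. Protocol Section 7.5.5.3 undertakes to explore the effect of ADAs on safety. Table 14.3.1.14 is the only AE table in the index that is broken down by ADA status, so it is where a reader will look for that effect.

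**Working it through.** The documents give no figure for this analysis and no sample size or event target, so there is nothing to reproduce. The check asks what the table would show if antibodies had no effect.

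**Inputs from the documents**
- AE collection runs from first dose "up to Day 7 of Week 24 (End of Study) will be recorded on the AE eCRF page", which is 24 weeks (SAP Section 14.2).
- Status can change at the serum samples of Weeks 2, 4, 8, 12, 16, 20 and 24 (SAP Section 14.5).
- Six patients, three in each of two cohorts (SAP Section 4.1).

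**Assumptions, not in the documents**
- The TEAE rate is constant over time and the same in both statuses.
- The patient is negative at Baseline, converts at the pre-infusion sample of Week w and stays positive. Only these two statuses are considered.
- Conversion week is varied from 2 to 20. Rates of 0.1 to 0.5 TEAEs per patient-week are used where a rate is needed.

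**Step 1: event counts.** Negative weeks = w − 1. Positive weeks = 24 − (w − 1). Expected events = rate × weeks, so the rate cancels from the ratio.

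| Conversion at Week | Negative weeks | Positive weeks | Expected count ratio, positive:negative |
|---|---|---|---|
| 2 | 1 | 23 | 23 |
| 4 | 3 | 21 | 7.0 |
| 8 | 7 | 17 | 2.4 |
| 12 | 11 | 13 | 1.2 |
| 16 | 15 | 9 | 0.60 |
| 20 | 19 | 5 | 0.26 |

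**Step 2: patient percentages.** With Poisson events, the chance of at least one event is 1 − exp(−rate × weeks). For conversion at Week 4 (3 v 21 weeks), negative v positive:
- 0.1 per week: 0.26 v 0.88
- 0.25 per week: 0.53 v 0.99
- 0.5 per week: 0.78 v 1.00

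**Step 3: some patients never convert.** If three patients convert at Week 4 and three never do, negative time is 3 × 3 + 3 × 24 = 81 patient-weeks and positive time is 3 × 21 = 63. The expected count ratio is 63/81 = 0.78. With all six patients as denominator, the positive percentage cannot exceed 3/6 = 50%, whatever the antibodies do.

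**Step 4: after the change.** Take six patients converting at Week 4 and 0.25 TEAEs per patient-week. Negative: 6 × 3 = 18 patient-weeks, 4.5 expected events, rate 4.5/18 = 0.25. Positive: 6 × 21 = 126 patient-weeks, 31.5 expected events, rate 31.5/126 = 0.25. The rate ratio is 1.0, and under these assumptions it is 1.0 for every conversion week.

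**The case against.** The case for leaving the table alone has real substance.

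- **No comparison is planned.** The SAP attaches no test, ratio or difference to this table. Six patients split by cohort, SOC, PT and four statuses leave very small cells. This stands and limits the impact, but readers will still set the columns side by side.
- **The timing is shown elsewhere.** SAP Section 14.5 plans a figure per patient in which titer and TEAEs run over time and ADA status is marked. Listings of AEs, serum immunogenicity and drug administration are also planned. With six patients this goes far towards exposing the problem, but it gives the table no denominator.
- **The cohort denominator is only a default.** SAP Section 8 allows exceptions, and SAP Section 19 says footnotes may clarify a percentage's denominator. The table shell is not in the documents. A reader might infer that the plan requires percentages over patients never in the status; the text supports that only as the default.
- **Rates are not clean either.** Protocol Table 1 keeps patients in hospital through the first three infusions, and vital signs are taken more often in Weeks 1 to 8. Negative time is likely to be early and closely observed, so a rate stays confounded with time on treatment. This stands and must be footnoted.

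Two stronger readings are tempting. One is that the primary endpoint is compromised because it consists of TEAEs and SAEs. The dose-cohort tables do not use the ADA split, so they are unaffected. The other is that the table inflates antibody risk, by sevenfold for instance. Seven is the result for one assumed conversion week; later conversion reverses the direction.

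**Conclusion.** The point holds as a limited one. As specified, Table 14.3.1.14 splits events by a time-varying status and provides no time at risk per status. Under a constant event rate and no antibody effect, the expected positive-to-negative count ratio runs from 23 (conversion at Week 2) to 0.26 (Week 20) for a patient who converts and stays positive. The table can thus exaggerate or hide an ADA association. The count ratios do not depend on the assumed rate, but they do depend on the assumed conversion week, on persistence and on the constant rate.

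The consequence is confined to one descriptive table in six patients. The programme has been discontinued and Cohort 3 will not start (SAP Section 4.1), so no escalation to that cohort turns on it. This is a cheap improvement, not a flaw in the main safety analysis.

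**What to change.** 1. State one rule in SAP Section 14.2 for ADA status between samples, for example carrying forward the status at the most recent sample. Use it both to classify events and to compute time at risk. Some such rule is needed anyway to classify the events. Carrying forward counts events that fall after true conversion but before the first positive sample as negative; the matching weeks are treated the same way.
2. Add to Table 14.3.1.14, per status: the number of patients ever in it (as the percentage denominator), patient-weeks, number of infusions, and overall TEAEs per patient-week. Rates by preferred term are not needed at this sample size.
3. Footnote that the rates remain confounded with time on treatment and with closer early observation, and should be read with the patient plots.

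The inputs (infusion dates, AE dates and ADA samples) are already collected. The cost is a small amount of extra programming and one added convention.
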